#### 9.4.2 Intensive PK Analysis

PK parameters for each subject will be estimated using non-compartmental analysis (NONCMP) and follow a linear up-log down trapezoidal rule in conjunction with first-order input (WinNonlin). PK parameters, including the elimination rate constant  $\lambda_z$  and  $t_{1/2}$  will be estimated, with  $t_{1/2}$  calculated as  $\ln_2/\lambda_z$ . AUC will be estimated as the  $AUC_{0-8h}$  or  $AUC_{0-24h}$  (as results permit) for artemether/DHA and the sum of  $AUC_{last}$  (AUC to the

end of the sampling period) and  $AUC_{last-\infty}$  (from the end of sampling to infinity) for lumefantrine/ desbutyl-lumefantrine. PK parameters will be compared between groups of interest (Figure 1 and Table 8) using a two-sided unpaired t-test for two-group comparisons, and ANOVA for multi-group comparisons. If PK parameters are found to have skewed distributions and data transformations do not induce symmetry, rank-based tests will be used. To enhance comparison between 3-day and 5-day AL, peak concentrations collected on Days 0-4 will be integrated using population methods. The following groups will be compared:

**Table 8. Primary objectives and comparator groups for intensive PK study**

Primary Objectives	Comparison Groups
Impact of 5-day vs 3-day AL on AL exposure in HIV-infected children on EFV-based ART	HIV-infected children on EFV-based ART 3-day AL (n=30), vs. HIV-infected children on EFV-based ART 5-day AL(n=30).
Impact on AL exposure of 5-day AL in HIV-infected children on EFV-based ART vs 3-day AL in HIV-uninfected children	HIV-infected children on EFV-based ART 3-day AL (n=30), Vs. HIV-uninfected children 3-day AL (n=30, age 3-18years).
Impact of 5-day vs 3-day AL on AL exposure in HIV-uninfected children	HIV-uninfected children 5-day AL (n=50), vs. HIV-uninfected children 3-day AL (n=50).

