#### HYPOTHESES:

- 1) 5-day AL will provide superior PK exposure and improved treatment outcomes compared to 3-day AL in HIV-infected EFV-treated children
- 2) 5-day AL in HIV-infected EFV-treated children will provide comparable PK exposure and outcomes to 3-day AL in HIV-uninfected children.
- 3) 5-day AL in HIV-uninfected children will provide superior PK exposure and improved treatment outcomes as compared to 3-day AL in HIV-uninfected children.

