## 2.0 STUDY OBJECTIVES

### 2.1 Primary Objectives:

- 1) To evaluate and compare the PK exposure between 5-day AL treatment and 3-day al treatment in HIV-infected children on EFV-based ART
- 2) To evaluate and compare the PK exposure of 3-day and 5-day AL treatment in HIV-infected children on EFV-based ART to 3-day AL treatment in HIV-uninfected children not on ART.
- 3) To evaluate and compare the PK exposure of 3-day and 5-day AL treatment in HIV-uninfected children not on ART.
- 4) To evaluate the pharmacodynamics of AL in the context of extended dose regimens and HIV infection.

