## 9.0 STATISTICAL CONSIDERATIONS

### 9.1 General Design Issues.

This is a prospective study to evaluate the PK and PD of extended dose AL in the context of EFV-based ART and in the context of HIV-uninfected children and to characterize the impact of a 5-day regimen on AL PK/PD as compared to the standard 3-day regimen; the study will be conducted in Uganda.

The current proposal will study the PK/PD of AL in HIV-infected children on EFV-based ART and HIV-uninfected children not on ART either enrolled at TDH or MGH. We will compare the PK of 5-day AL in HIV-infected children on EFV-based ART to 1) 3-day AL in HIV-infected children on EFV-based ART, and 2) 3-day AL in HIV-uninfected children. In addition, we will compare the PK of 5-day AL in HIV-uninfected children to 3-day AL in HIV-uninfected children. Comparisons will be based on an intensive PK design for AL AUC estimations in 30 to 50 subjects for each of the study groups. Study group comparisons will be controlled for age (i.e. results for HIV infected children on EFV-based ART who are 3-10 years of age, will be compared to results for HIV uninfected children who are also 3-10 years of age). The proposal will also study the impact of AL exposure on treatment outcomes and adverse events using a population PK/PD design. This will involve population PK study of up to an additional 100 HIV-infected children and 120 HIV-uninfected children.

*Although an individual child is eligible to enroll in both the intensive PK study and the population PK study for separate episodes of malaria, there is no assurance that the same child will contribute to both study components. Thus, it is possible that the total number of subjects for all groups may be as high as 380.*

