### 9.4 Intensive PK study

#### 9.4.1 Sample Size

Using measures of mean AUC and its coefficients of variation (CV) from our studies and the literature, the intensive arms of the study are powered to detect differences in ACT AUC between all study groups (3-day AL vs 5-day AL) with  $n=30$  for each group of HIV infected children. To assure adequate age-matched HIV uninfected children,  $n=50$  is used for the group of HIV uninfected children. Figure 1 and Table 8. 50 HIV-uninfected children provides for adequate subjects  $< 3$  years and  $\geq 3$  years of age as HIV-infected children receiving EFV-based ART is restricted to  $\geq 3$  years of age. In addition, the same size of 50 will permit PK/PD of the extended regimen in younger children  $< 3$  years of age. At least 30 HIV uninfected children must be between 3-10 years of age.

For comparisons where  $n=30$  in both groups, there will be 80% power to detect a difference in AUC of 35% or more, given an overall Type I error of 0.05, a Bonferroni correction for multiple comparisons, and with assumption that the coefficient of variation (CV) for all AUC's is 35-38%. For the HIV-uninfected children with  $n=50$ , further distinctions based on age can be determined as well as further enhancement of exposure-response analysis.

Although many children are likely to be studied for both the 3-day and 5-day regimens, it is not likely that *all* children will provide results for both. However, all analyses will account for repeated measures/correlated data that occur from participants enrolled into multiple arms.

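### Table 8 row 2 lists the 3-day HIV-infected arm under a 5-day label, and the AUC test named in 9.4.2 assumes independence although a child may contribute two intensive episodes

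*Combined protocol and SAP*

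**What the plan says.** **Table 8 (9.4.2).** The objective label of row 2 is "Impact on AL exposure of 5-day AL in HIV-infected children on EFV-based ART vs 3-day AL in HIV-uninfected children". The groups printed beside it are "HIV-infected children on EFV-based ART 3-day AL (n=30), Vs. HIV-uninfected children 3-day AL (n=30, age 3-18years".

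**Other statements of the contrast.** Hypothesis 2 in the Schema is that "5-day AL in HIV-infected EFV-treated children will provide comparable PK exposure and outcomes to 3-day AL in HIV-uninfected children". Primary objective 2 (2.1) compares "3-day and 5-day AL treatment in HIV-infected children on EFV-based ART to 3-day AL treatment in HIV-uninfected children", so it covers both infected regimens. Section 9.1 sets 5-day AL in infected children against two comparators: "3-day AL in HIV-infected children on EFV-based ART, and 2) 3-day AL in HIV-uninfected children".

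**Test for AUC.** Section 9.4.2 compares PK parameters "using a two-sided unpaired t-test for two-group comparisons, and ANOVA for multi-group comparisons", with rank-based tests if transformation does not remove skewness.

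**Repeat episodes.** The Schema (Sample Size footnote and Study Duration) allows two intensive episodes per child. Under 3.2.3 each episode is randomised, so the second may fall on the same regimen or the other one. Section 9.4.1 adds that "all analyses will account for repeated measures/correlated data that occur from participants enrolled into multiple arms", and sets power "given an overall Type I error of 0.05, a Bonferroni correction for multiple comparisons" without giving the number of comparisons. Section 9.5.2 names robust sandwich estimators for the Cox outcome models because a child may enter more than once.

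**The concern.** The table that lists the groups for the primary AUC comparisons pairs a 5-day label with a 3-day arm. An analyst who works from the groups column would run a real primary contrast, but not the one the row announces. The contrast that tests hypothesis 2 would then have no listed groups, sample size or place in the multiplicity count.

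An unpaired t-test or ANOVA treats every AUC as independent. Two episodes from one child are likely to be correlated. Two in the same arm make the test's standard error too small; one in each arm makes it too large for the comparison of those arms. The 9.4.1 commitment points the right way, but it names no method, refers only to children in more than one arm, and is not carried into 9.4.2.

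**Working it through.** **1. Row 2 against the rest of the plan**

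| Place | Infected arm | Uninfected arm |
|---|---|---|
| Table 8 row 2, label | 5-day | 3-day |
| Table 8 row 2, groups | 3-day (n=30) | 3-day (n=30) |
| Hypothesis 2 | 5-day | 3-day |
| Primary objective 2 | 3-day and 5-day | 3-day |
| 9.1 | 5-day | 3-day |

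Rows 1 and 3 compare regimens within one population, so neither supplies the missing entry. Objective 2 contains two contrasts; the label of row 2 states one and its groups cell the other.

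The two are not interchangeable. As an illustration, Table 1 gives a lumefantrine AUC ratio of 130/270 = 0.48 for 3-day AL with EFV against control. Applying the 1.7-fold increase anticipated in 9.5.1 gives 130/270 × 1.7 = 0.82. At 30 v 30, level 0.05/3 and CV 35-38% (log scale, noncentral t), a difference test has about 37-43% power at 0.82 and essentially 100% at 0.48.

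**2. The stated power**

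Inputs from 9.4.1: 30 per group, 35% difference, CV 35-38%, overall 0.05 with Bonferroni. Scale and divisor are not stated. On the log scale, SD = √ln(1+CV²) = 0.340 or 0.367 and the effect is ln 1.35. Noncentral t gives 80.4% with two comparisons at CV 38%, and 79.6% with four at CV 35%. On the raw scale, six comparisons at CV 38% give 79.4%. The 80% is therefore reproducible, and entering the 5-day arm leaves 30 v 30 unchanged.

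**3. The unpaired test with repeat episodes**

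Assumptions, since the documents give no values: within-child correlation ρ of 0.3 to 0.7, 60 episodes per population with 30 in each arm, and each episode randomised. If a fraction f of children repeat, the number of children is 60/(1+f). That gives 48, 40 or 30 children, of whom m = 12, 20 or 30 give two episodes, for a quarter, half or all repeating.

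The expected number of same-child pairs in a given arm is s = m × (30/60) × (29/59). The variance of an arm mean is multiplied by V = 1 + 2sρ/30. The two populations are independent, so V also applies to the infected-uninfected difference. Actual error is approximately 2·P(t₅₈ > 2.002/√V).

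| Repeating | m | s | V, ρ = 0.3 to 0.7 | Error, formula | Error, simulated (40,000 runs) |
|---|---|---|---|---|---|
| Quarter | 12 | 2.95 | 1.06-1.14 | 5.7-6.6% | 5.7-6.7% |
| Half | 20 | 4.92 | 1.10-1.23 | 6.1-7.6% | 6.1-7.9% |
| All | 30 | 7.37 | 1.15-1.34 | 6.7-9.0% | 6.6-9.2% |

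At 0.05/3 (nominal 1.7%, divisor assumed) the simulated errors are 2.1-2.5%, 2.3-3.1% and 2.4-3.8%.

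*5-day against 3-day within a population.* Same-arm pairs add variance and cross-arm pairs remove it. The variance ratio is [60 + 2ρ(2s) − 2ρ(m − 2s)]/60, which lies between 0.988 and 0.998 in these settings. The two effects almost cancel, and the simulated error is 4.8-5.1%.

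*Crossover repeats only.* If k children give one episode to each arm, V = 1 − kρ/30. Simulated error is 4.0% falling to 2.5% for k = 10, and 3.4% falling to 1.6% for k = 15, as ρ rises from 0.3 to 0.7. The test is then conservative and loses power.

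The documents do not settle which pattern will occur. Sections 3.1.2 and 3.2.2 describe both regimens or a crossover; 3.1.1, 3.2.1 and 3.2.3 describe re-randomisation.

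**The case against.** **Row 2 is a one-cell slip.** The contrast is stated in the row's own label, hypothesis 2, objective 2 and 9.1, and 9.4.2 also relies on Figure 1, which is not reproduced in the text available. This stands. A reader might infer that the plan has dropped the hypothesis 2 contrast, or that the printed 3-day contrast is a mistake to be overwritten. Neither is supported: the first contrast is stated in four places, and the second is part of primary objective 2.

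**Correlation is already committed to.** Section 9.4.1 says so for all analyses, and arm may be meant loosely there. A reader might infer that the plan ignores repeat episodes, and that would be wrong. What remains is that 9.4.2 then names a test that assumes independence. The mixed-effects PK model in 9.5.2 does separate within- and between-child variability, but it is described as reinforcing the primary objectives, not as replacing the AUC comparison.

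**Harm is not established.** The test may be liberal, correct or conservative; 9.4.1 expects many children to be studied on both regimens, which points towards conservative for 5-day against 3-day. The 9% figure needs every child to repeat at correlation 0.7. This also stands, so the case for change rests on the conflict in the text rather than on the simulated error rates.

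**The missing divisor does not undermine power.** Agreed. Because 80% can be reached under ordinary choices, the documents do not support a claim that the study is underpowered for its stated 35% difference.

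**Conclusion.** Both defects hold as matters of text. The label and groups of Table 8 row 2 disagree, which leaves the groups column without an entry for the hypothesis 2 contrast. Section 9.4.2 names an independence-based test for the primary AUC comparisons that conflicts with 9.4.1 and with the allowance of two intensive episodes per child. The 9.4.1 wording does not clearly reach repeats on the same regimen, and a clustered method for comparing groups is named only for the Cox models.

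The statistical effect is modest and its direction is not fixed. It rests on the assumed repeat fractions, correlations and equal arms set out above. A general claim of inflated type I error would go too far: inflation applies to infected against uninfected under re-randomisation, not to the within-population comparison and not to crossover repeats. Two neighbouring matters are separate from this point: whether a difference test can support comparable exposure, and the 3-10 against 3-18 year age ranges. The point should be fixed before analysis; it does not call for a change in design or sample size.

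**What to change.** **(a) Table 8.** For row 2, enter HIV-infected 5-day (n=30) against HIV-uninfected 3-day (n=30). Keep 3-day infected against 3-day uninfected in a row of its own, because primary objective 2 includes it. Count both in the Bonferroni correction and state the divisor in 9.4.1.

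**(b) 9.4.2 and 9.4.1.** Replace the unpaired t-test and ANOVA with a mixed model on log AUC, or GEE with robust variance, with child as the cluster. Report geometric mean ratios with confidence intervals. Extend the 9.4.1 sentence to repeat episodes on the same regimen. This handles either pattern of repeats.

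**Cost.** Wording and a little more analysis work; no new data or visits. If four contrasts are counted instead of three, the level moves from 0.05/3 = 0.0167 to 0.05/4 = 0.0125. For a 35% difference, power then moves from 82.6% to 79.6% (CV 35%) or 75.6% to 72.0% (CV 38%) on the log scale, and from 91.7% to 89.8% or 86.1% to 83.5% on the raw scale.

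Simulations of a random-intercept model without an age term (ratio 1.35, CV 38%, 0.05/3, half or all children repeating, re-randomised) show no overall gain for infected against uninfected: 70-78%, against 73-76% for the unpaired test. Power for 5-day against 3-day rises from 75-77% to 79-97%. The model's type I error at nominal 5% was 4.6-5.9%, so it is close to its level but not exact.

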## 9.5 Population PK study

### 9.5.1 Sample Size

160 episodes of malaria in HIV-infected children and 220 episodes of malaria in HIV-uninfected children (up to 4 episodes per child including up to 2 involving intensive sampling) are more than sufficient to obtain population PK parameter estimates for both groups of children with good precision. Outcomes will be assessed in children in both the intensive and population PK studies, as such, sample sizes reflect the sum of children enrolled in each arm for each type of PK sampling. Thus, total sample sizes will be 80 to 110 children per arm. Using WinPOPT®, the standard errors (SE) of all population PK parameters, including variability parameters, will be <20% of their means, except for the interindividual variability of  $k_a$ , for which the SE is estimated to be 32% of its mean. Based on our recent study from Tororo, where a 42-day recurrence rate of 47% was observed in those on EFV-based ART, we will have 80% power to detect a 20% difference in recurrence rates between 3-day and 5-day arms. Notably, in our previous exposure-outcomes, with 50 to 70 children in each ART arm and 184 children not on ART, a 2.1-fold change in AUC between those on EFV and lopinavir/ritonavir translated to a 2.7-fold increase in risk for reinfection. In other words, the anticipated increase in AUC between 5-day and 3-day AL of 1.7-fold increase in exposure is expected to translate to a clinically relevant change in risk in a similar number of subjects.

### 9.5.2 Population PK Analysis and Correlation of AL PK with treatment outcomes.

Population PK analysis will utilize both intensive and sparse PK sampling data for both HIV infected and HIV uninfected children. Plasma concentrations will be transformed

into natural logarithms and concentration-time profiles will be analyzed using non-linear mixed effects (NLME). For NLME modeling, PK data will be analyzed using a standard PK model formalism. To analyze population data the PK model is embedded in a two-stage NLME model, accounting for both intra- and inter-subject variability. The estimation of NLME parameters will be accomplished using the software NONMEM (version 7; Icon Development Solutions, Maryland), in particular the first order conditional estimation method with interaction that uses a linear approximation to the likelihood of the data. Diagnostic graphics and post-processing of NONMEM output and simulations will be performed using the statistical software R. Model development will be guided by exploratory analysis of the data, changes in the NONMEM objective function value, and diagnostic plots. Our recent lumefantrine modeling suggest a two- and three-compartment model provide the best fit, respectively, though additional models will be tested Alternative models for intra-subject variability (proportional and constant plus proportional) will be explored as appropriate. To reinforce the primary objectives, base model building will also include quantification and formal test of the impact of EFV on PK of AL. Specifically, the impact of HIV treatment will be tested as potential covariate on clearance and/or bioavailability. Further stepwise covariate analysis will be performed to identify the impact of covariates on the PK of AL with special focus on the impact of markers of malnutrition, as measured by weight, BMI, and various Z scores and mid-arm circumference. Other covariates will include age, body size (weight, height), concomitant medications, parasitemia, hematocrit, and CD4 count (for HIV-infected children). Both linear and nonlinear relationship between continuous covariates and model parameters will be investigated in a stepwise fashion. Subject-specific estimates of artemether, DHA, lumefantrine, and desbutyl-LR exposure will be obtained from individual PK analyses for subjects with intensive PK sampling (AUC) and a posteriori from population PK analysis (as given by dose/(CL/F)). These estimates will be used to test for a significant relationship between drug exposure and the primary treatment outcome (recurrent infection at day 28-42 using standard WHO treatment outcomes) using Cox proportional hazard models with robust sandwich estimators that account for correlated data, as individuals may be enrolled for multiple episodes of malaria. A secondary outcome will be sub-patent infections detectable by LAMP, which will also be analyzed for associations with PK exposure using Cox models. Simultaneous PK/PD analysis will be performed to maximize the entire database. As for PK, we will investigate if there is any potential impact of indices of malnutrition, HIV status, age and other covariates on PD parameters. In other words, we will identify if target concentrations to prevent reinfection might be altered in different patient population due to known covariates. Once targets are identified, population PK models will be used to simulate different AL PK dosing approaches to identify optimized regimens that ensure concentrations are maintained within the concentration range necessary to maximize efficacy in all studied populations.

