**1.1.3 Malaria and HIV in Uganda.** Uganda bears a heavy burden of both malaria and HIV. Although malaria prevention and control programs have reduced infections and mortality overall, Uganda still has one of the highest malaria transmission intensities in the world. In Tororo, the site of this proposal, children experience up to 2 to 6 malaria episodes per year, despite usage of bed nets and trimethoprim-sulfamethoxazole (TS) for those HIV-infected. For HIV, Uganda is lauded for prior success in stemming the HIV epidemic, but new infections are now on the rise. It is estimated that 2 million HIV-infected children will reside in sub-Saharan Africa in 2020. Thus, HIV-malaria co-infection remains common, with treatment complicated by multiple pharmacological factors that require field-based studies, such as those currently proposed in this renewal.

**1.1.4 Significant drug interactions occur between ART and ACT.** Both components of AL are extensively metabolized. Artemether undergoes rapid demethylation by cytochrome p450 3A4 (CYP3A4) and CYP2B6 to the active metabolite,

dihydroartemisinin (DHA), which undergoes further metabolism via UDP-glucuronosyltransferases (UGT). CYP3A4 is also responsible for metabolizing lumefantrine to desbutyl-lumefantrine (desbutyl-LR), and was shown by our group to be

Table 1	Comparison of AL PK exposure in HIV-infected children on ART compared to HIV-uninfected children (controls)		
	HIV-uninfected	HIV-infected	
	AL alone (control)	AL+EFV	
	GM; 95%CI (n=52)	GM; 95%CI (n=31)	GMR, EFV/Control
AR_AUC 0-8	120 (97.6-147) a	48.5 (37.2, 63.1)	0.40***
DHA_AUC 0-8	212 (176, 256) a	62.9 (49.2, 80.3)	0.30***
LR_AUC 0-∞	270 (232, 313)	130 (107, 157)	0.48***
LR Half-life b	64.3 (52.0, 121)	23.7 (21.8, 46.0)	0.37***
Intensive and sparse PK (n=363 episodes)			
	Median (IQR), n=186	Median (IQR), n=48	MR, EFV/Control
LR C 7d	340 (257, 531)	111 (63, 192)	0.30***
LR C 14d	86 (59, 137)	BLQ (BLQ,BLQ)	<1***
LR C 21d	BLQ (BLQ, 63)	BLQ (BLQ,BLQ)	<1**

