## **6.7.2 Population pharmacokinetic study**

For children participating in the population PK sampling, AL treatment will be 6 or 10 doses of Coartem® (provided by the study) administered over 3 or 5 days: Study Days 0, 1, and 2 or Study Days 0,1,2,3 and 4, *Capillary* samples for lumefantrine only (200 µL) will be collected on Study Day 0 (prior to AL administration). *Capillary* samples for artemether/DHA and lumefantrine (200 µL\*) will be collected by finger prick on Study Days 0-2 (3 day AL) or 0-4 (5 day AL) at approximately 2 and 4 hours post-dose. In a subset of children, *capillary* samples for artemether/DHA and lumefantrine (200 µL\*) will be collected by finger prick on Day 2 in the 3-Day regimen and on Day 4 in the 5-Day regimen, prior to AL administration. On Study Days 3 (3 day AL) or 5 (5 day AL) at approximately 24 hours post-last dose, an additional capillary sample will be taken. In addition, *capillary or venous* samples will be collected for lumefantrine only on Study Days 7, 14, 21. Subjects with repeat infection during the 42-day follow-up will provide an additional PK sample at the time of repeat infection.

\*200 µL *capillary* samples will be collected by finger prick and can be used to measure all 3 analytes but without the ability to do repeat analysis if necessary. 500µL *venous* samples permits repeat analysis as needed.

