### **6.7.4 Assays for artemether, DHA and lumefantrine**

Artemether, DHA and lumefantrine and active desbutyl-lumefantrine will be measured using optimized methods validated in our laboratory. All methods will utilize liquid chromatography tandem mass spectrometry.

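### Section 9.5.2 names only FOCE with interaction on log concentrations and gives no quantification limit or rule for BLQ samples, although Table 1 predicts mostly BLQ lumefantrine at Days 14 and 21 in EFV children

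*Combined protocol and SAP*

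**What the plan says.** Section 9.5.2 (Population PK Analysis) takes plasma concentrations "into natural logarithms and concentration-time profiles will be analyzed using non-linear mixed effects (NLME"). Estimation is in NONMEM version 7, "in particular the first order conditional estimation method with interaction that uses a linear approximation to the likelihood of the data". No other estimation method is named.

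For population PK children, section 6.7.2 plans that "samples will be collected for lumefantrine only on Study Days 7, 14, 21". Section 6.7.1 plans the same for intensive PK children on Days 8, 14 and 21.

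The individual exposures come from individual PK analysis (intensive children) or "a posteriori from population PK analysis (as given by dose/(CL/F")). Section 9.5.2 then states: "These estimates will be used to test for a significant relationship between drug exposure and the primary treatment outcome". The same section uses the model to look for concentrations that prevent reinfection and to simulate dosing approaches.

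On the assay, section 6.7.4 says only that the analytes "will be measured using optimized methods validated in our laboratory". No section gives an LLOQ or says how BLQ results enter the population model.

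**The concern.** Table 1 (section 1.1.4) gives lumefantrine in the EFV group as BLQ at the median and at both quartiles on Day 14 and on Day 21, and the control median on Day 21 is also BLQ. So two of the three late samples per EFV child will probably be BLQ. A BLQ result has no logarithm, and FOCE with interaction supplies no likelihood for a censored value. An analyst who follows 9.5.2 literally must drop these records or put a number in their place.

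Dropping them leaves a selected set of late samples, weighted toward slow eliminators. Substituting a number near the LLOQ places a point far above the true concentration. Either way the fitted decline is too slow. What is at stake is the terminal phase and what depends on it: exposure in the lowest-exposure children, its relation to recurrence, and the simulated targets and regimens.

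**Working it through.** **Inputs from Table 1** (earlier data, headed "Intensive and sparse PK (n=363 episodes")). EFV, n=48: Day 7 median 111 (IQR 63, 192), Days 14 and 21 BLQ throughout the IQR, half-life 23.7 (21.8, 46.0), AUC 130. Control, n=186: Day 7 median 340, Day 14 86 (59, 137), Day 21 BLQ (BLQ, 63), half-life 64.3, AUC 270. No units are given; ng/mL for concentrations and µg·h/mL for AUC are assumed.

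**Reproducing the table.** Half-life ratio 23.7/64.3 = 0.369 (stated 0.37). AUC ratio 130/270 = 0.481 (stated 0.48). The Day 7 ratio of medians is 111/340 = 0.33 against a stated 0.30; nothing below uses it.

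**How many samples are BLQ?**
- An upper quartile that is BLQ means at least 75%, so at least 36 of 48 EFV episodes at each of Days 14 and 21. A BLQ control median at Day 21 means at least 50%.
- Projection from the EFV Day 7 median: 111 × 2^(−168/23.7) = 0.8 at Day 14. With the upper half-life of 46.0 it is 111 × 2^(−168/46.0) = 8.8. Both lie far below the lowest quantified Table 1 figure, 59, which also caps the earlier LLOQ at about 59.
- At Day 7, log-SD = ln(192/63)/1.349 = 0.826. P(BLQ) = Φ((ln LLOQ − ln 111)/0.826) = 4% at LLOQ 25, 17% at 50 and 22% at 59.

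**Effect on the EFV half-life.** Simulation of a log-linear terminal phase: 80 children, samples 24, 120, 288 and 456 h after the last dose, Day 7 median and spread as above, residual SD 0.25 on the log scale, six replicates per row. All fits used quadrature, so the rows compare BLQ handling, not FOCE itself. Fitted half-life in hours:

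| True half-life | Variability in k | LLOQ | BLQ dropped | First BLQ = LLOQ/2 | BLQ censored |
|---|---|---|---|---|---|
| 23.7 | 20% | 20 | 23.9 (+1%) | 36.7 | 23.8 |
| 23.7 | 20% | 50 | 25.3 (+7%) | 44.2 | 23.6 |
| 23.7 | 35% | 20 | 25.6 (+8%) | 37.8 | 23.3 |
| 23.7 | 35% | 50 | 28.5 (+20%) | 44.5 | 24.5 |
| 35 | 35% | 20 | 36.5 (+4%) | 44.9 | 35.2 |
| 35 | 35% | 50 | 41.4 (+18%) | 54.5 | 35.0 |
| 46 | 30% | 20 | 49.3 (+7%) | 55.7 | 46.6 |
| 46 | 30% | 50 | 51.0 (+11%) | 64.2 | 46.2 |

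Monte Carlo standard errors are 0.2 to 1.3 h, so the +1% row is indistinguishable from no bias. Substitution gives +21% (55.7/46) to +88% (44.5/23.7). The censored fit stays between −2% (23.3/23.7) and +3% (24.5/23.7).

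**Effect on exposure.** EFV AUC after Day 7 = C7 × half-life/ln 2 = 111 × 23.7/0.693 = 3.8 µg·h/mL, or 2.9% of 130. With half-life 46.0 it is 7.4, or 5.7%. A small simulation on the 3-day population schedule (ten post-dose samples, seven of them before Day 7; one compartment; LLOQ 20 to 50; 80 children; five replicates) found that dropping BLQ raised average exposure by 2% to 4% in EFV children and 2% to 6% in controls. In the lowest-exposure quartile it was +8% to +15%, against +2% to +5% with the censored likelihood.

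**Effect on predicted tail concentrations.** From 111 at Day 7, a half-life of 28.5 h instead of 23.7 h predicts 111 × 2^(−168/28.5) = 1.9 at Day 14 instead of 0.8, more than double, though both are very low.

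**Regimen.** Population PK children take the last dose on the evening of Day 2 or Day 4 (Appendix B, note 7), so every fixed-day sample comes about 48 h sooner on 5-day AL. At 23.7 h that is a factor 2^(48/23.7) = 4.1. With LLOQ 50 and no accumulation, Day 7 BLQ is about 17% on 3-day AL and Φ((ln 50 − ln(111 × 4.1))/0.826) = 0.4% on 5-day AL.

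**The case against.** The strongest reply is that this is an omission. Section 9.5.2 never says BLQ records will be dropped or imputed, it leaves structural and error models open, and a censored fit runs in the same NONMEM 7. That stands. A reader might infer that the plan discards BLQ samples and that half-life is therefore overestimated. The documents do not support this: the bias is conditional on a choice the plan has not made. But the one method it names cannot carry the censored information, so the gap is more than missing detail.

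A reader might also infer that the EFV-versus-control comparison is distorted. The calculations do not show it. A separate run at LLOQ 50 gave 26.1 h (true 23.7) on EFV and 70.1 h (true 64.3) in controls, a ratio of 26.1/70.1 = 0.372 against 0.369. Its control arm is itself doubtful: 340 × 2^(−168/64.3) = 56 at Day 14, whereas Table 1 reports 86, which implies a half-life nearer 168 × ln 2/ln(340/86) = 85 h.

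A third tempting reading is a spurious difference between regimens. The BLQ share may well differ, but Table 1 has no 5-day data, the figure above ignores accumulation, and the LLOQ is assumed. That supports reporting % BLQ by regimen, not a claim of arm bias.

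Finally, the Table 8 contrasts use non-compartmental AUC with t-tests or ANOVA (section 9.4.2), and intensive children enter the recurrence analysis through their individual AUC. That also stands. The average exposure bias is small beside the roughly two-fold EFV effect in Table 1 and the 1.7-fold regimen effect anticipated in section 9.5.1.

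**Conclusion.** The point holds as a gap in the population model. The plan names one estimation method without a censored-data likelihood and sets no LLOQ or BLQ rule, while its own Table 1 predicts that at least three quarters of EFV lumefantrine samples at Days 14 and 21, and at least half of control samples at Day 21, will be BLQ.

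If those records are dropped, the typical EFV half-life is biased upward by roughly 1% to 20%; LLOQ/2 substitution is worse. Average exposure shifts by a few percent, with more in the lowest-exposure children. The consequences lie in the terminal phase, the exposure-recurrence analysis and the target-concentration and regimen simulations. They do not reach the Table 8 AUC contrasts.

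These sizes rest on an assumed LLOQ of 20 to 50, a one-compartment or single-exponential decline, assumed variability, few replicates, and earlier-study episodes standing in for this trial's children. Section 9.5.2 expects two- or three-compartment models, so the direction is firmer than the exact percentages.

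**What to change.** In section 9.5.2:
- State the lumefantrine LLOQ.
- Make the primary lumefantrine population model one that keeps BLQ samples as censored observations (M3 likelihood, by the Laplacian method or SAEM, both available in NONMEM 7).
- Report % BLQ by visit, HIV group and regimen.
- Keep the FOCE-with-interaction fit with BLQ records dropped as a sensitivity analysis, and name it as the fallback if the M3 fit does not converge.

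The cost is plan wording, longer run times and possible convergence difficulty. No new samples or visits are needed. Settling the rule before concentrations are seen also removes a later choice that could move the exposure-recurrence results.
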